6.0 STATISTICAL ANALYSIS

6.1 Primary and secondary endpoints.

The primary endpoint is difference in caregiver anxiety between the intervention and control groups at 20

weeks post-radiation treatment. Secondary endpoints are caregiver anxiety at the end of radiation treatment and 4 weeks post treatment; caregiver depression, HRQOL, and fatigue at the end of treatment and 4 weeks post-treatment; and patient HRQOL at the end of treatment and 4 weeks post-treatment.

6.2, 6.7, 6.8 Statistical Design, Power, Analysis plan, & Missing data.

An intent-to-treat analysis is planned. Before carrying out inferential statistical procedures, exploratory data analysis will be performed: all variable distributions will be examined and descriptive summary statistics will be provided: including means, standard deviations, and ranges for continuous variables, as well as percentages and frequencies for categorical variables, will be provided to describe the study sample. Variable transformations will be made in cases where distributions are skewed, or otherwise fail to meet the assumptions for analyses; nonparametric procedures will be used where transformations would be inappropriate. Plots will be used to describe the data and identify outliers and influential observations.

Aim 1

Analysis. The primary analysis for Aim 1 will be to compare the control and CG intervention arms with respect to CG anxiety at T4 (20 weeks postradiation treatment). A linear mixed model repeated measures analysis will be used to obtain mean changes from baseline in anxiety scores at Times T2, T3, and T4, using baseline anxiety as a covariate, also adjusting for covariates described in Table 4. A contrast of means will be constructed to compare arms with respect to change in anxiety at T4 (primary analysis) at the 0.05 significance level. In addition, the baseline characteristics of the two treatment groups will be compared using appropriate 2-sample tests for continuous or binary outcomes, and in a secondary analysis, characteristics found to differ between groups at baseline will be adjusted for in the linear mixed model. A secondary analysis will test for differences between groups at the other postbaseline time points, using the Tukey method to control the familywise error rate on a per outcome basis. Other CG outcomes will be compared between groups using a similar approach.

Power. With 180 subjects randomized and a 10% dropout rate, the sample size for the primary analysis will be 162 CGs (81 per arm). Assuming a correlation of 0.50 between CG anxiety scores at baseline and T4, when adjusting for baseline anxiety, a difference in means of 0.36 standard deviations (*SDs*) can be detected with 80% power using a 2-sided test with significance level 0.05, where *SD* is the within-group standard deviation of anxiety scores at Time T4. Here, adjustment for baseline anxiety reduces the detectable effect size from 0.41 to 0.36. This effect size (Cohen's *d*) is intermediate between a "small" (0.2) and "moderate" effect size, as defined by Cohen,¹⁰⁶ and is close to the pooled estimate of 0.29 from a meta-analysis of interventions (psychoeducational, skills training, and therapeutic counseling) with family CGs of cancer patients.² For other outcomes, there is 80% power to detect effect sizes of 0.41 *SDs* with a 2-sided test, significance level 0.05.

Aim 2

Analysis. This aim is to measure the effect of the intervention, as compared to a control group, on patient outcomes (HRQOL, interrupted treatment course) and healthcare utilization outcomes (unplanned hospital admissions, unplanned emergency room visits, and unplanned IV fluid use). Most outcomes will be count variables enumerating the cumulative numbers at T2, T3, and T4, which can be analyzed using Poisson regression methods implemented as generalized linear models, possibly allowing for overdispersion. Zero-inflated Poisson or negative binomial models^{107,108} will be considered if the data indicate a higher frequency of zeros than predicted by a Poisson model. HRQOL, a continuous measure, will be analyzed using a linear mixed model with repeated measures at T1, T2, T3, and T4. We will analyze the effect of the intervention on HRQOL across diagnoses using the common FACT subscales and will describe the symptom experience within each diagnostic group using the cancer-specific FACT subscale.

Power. From our pilot study, in the control group we expect means of 0.29 and 0.25 for the number of unplanned missed days and number of unplanned hospital admissions, respectively. In a Poisson regression model, sample sizes of 81 patients per group will provide 80% power to detect a 68% reduction in unplanned missed days and a 72% reduction in unplanned hospital admissions in the intervention group compared to the control group (2-sided test, significance level 0.05).

Aim 3

Analysis. This aim focuses on estimating and testing the mediating effects of family CG self-efficacy on their anxiety at Time T4 and other time points. The analysis will follow a standard (Baron-Kenny) approach of first testing the associations between intervention and the mediator (self-efficacy), and between self-efficacy and the outcome (anxiety) controlling for the intervention. If both associations are significant, the indirect effect of the mediator is estimated as the difference in the intervention effect on the anxiety before and after adjusting for the mediator.¹⁰⁹⁻¹¹¹ The standard error of the indirect effect, used to construct a confidence interval, can be estimated using a marginal regression approach with standard generalized estimating equations software, or using a bootstrap approach.¹¹¹

Power. If the effect size (difference in means of intervention vs. control groups divided by within-group standard deviation) is 0.40 for anxiety at T4, and is 0.50 for CG self-efficacy at T4 and the correlation of self-efficacy and anxiety at T4 is 0.40, the difference in means in anxiety after adjusting for the self-efficacy is reduced to an effect size of 0.20 SDs (i.e., the indirect effect of self-efficacy is 0.20, or 50% of the total). Simulations with n=10,000 replications showed in this scenario that the proposed approach had 81% power for testing that the indirect effect is zero (two-sided test, significance level 0.05). Increasing the indirect effect by increasing either the correlation or the effect of the intervention on self-efficacy results in higher power.

Aim 4

Analysis. This aim examines if patient illness factors, care demands, demographic factors, and/or use of mental health interventions during treatment moderate the relationship between the intervention and CG outcomes. Effects of potential modifiers of the treatment effect will be examined by including terms for the modifier by treatment interaction effect in the basic ANCOVA model used to test the primary hypothesis.

Power. Analyses for Aim 4 to examine moderating effects will be primarily exploratory in nature, since it is well-recognized that power for testing interaction effects is not high in trials that are powered to detect main effects, as is the case here.¹¹² When testing interaction of a binary factor occurring with frequency 0.5, power is 0.86 to detect an interactive effect size of 1.0 SDs (e.g., an intervention effect of 1.0 in one subgroup and an effect of 0.0 in the other), using a 2-sided test, significance level 0.05.

Aim 4a: Analyses for Aim 4a will examine if the SDH variables moderate the relationship between the intervention and caregiver outcomes. Effects of potential modifiers of the treatment effect will be examined by including terms for the SDH modifier by treatment interaction effect in the basic ANCOVA model used to test the primary hypothesis. The increase in enrollment from the extension study will provide additional power, as it is well-recognized that power for testing interaction effects is not high in trials that are powered to detect main effects, as was the case with the parent study. When testing interaction of a continuous SDH modifiers and the treatment, power is 0.81 to detect an interactive effect size of 0.40 standard deviations (SD) using a 2-sided test, significance level 0.05, for those measures that will be available in all subjects (e.g. Ohio Opportunity Index). For SDH measures that will only be available in the 96 extension study participants, we will be able to detect an interactive effect size of 0.59 at the same power and significance levels.

Aim 4b: Qualitative interviews will be audio recorded and transcribed, then verified for accuracy by research staff. Any identifiable information will be removed from transcripts, and each will be assigned a

study number. Deidentified data will be analyzed with NVIVO software using thematic analysis. First, the research team, including the PI, will read and reread 5 transcripts to develop a codebook using an inductive approach. Then, all transcripts will be coded by the research team using NVIVO to organize the data. Additional codes, and subsequently categories of codes will be identified. Clusters of categories converged into themes. Each transcript will be read and coded by three members of the research team for interrater reliability.

Aim 5

Analysis. We will assess costs associated with healthcare utilization in both intervention and control groups. Medicare reimbursement rates will be used to estimate costs regardless of the age or insurance of the participant. Using the DRG, diagnosis and procedure codes we will determine what Medicare “would have paid” for those services, and will use that as a proxy for cost. Cost of IV fluids will be estimated using wholesale acquisition cost. We will compute a healthcare utilization cost for each participant. Mean differences between the two groups will be analyzed using a two sample *t*-test for independent means. If necessary, data will be transformed to satisfy normality. In addition, we will describe costs associated with the intervention. Data regarding nurse time for preparation of the simulation and delivery of the intervention (in-person and phone contacts) will be collected prospectively during the study period. An hourly cost will be estimated according to hourly rates according to the Wage and Compensation Survey of the Bureau of Labor Statistics. Equipment costs will be measured. We will also determine costs related to the participants. CGs will be surveyed at each intervention contact (during radiation weeks 1 and 3, and at the end of radiation treatment) regarding: (1) any travel expenses for meetings with the intervention nurse and (2) time lost from work and activities due to the intervention, valued at 100% and 60% of the average hourly rate.

Power. A sample size of 81 in each group will provide 90% power of detecting a medium effect size (Cohen's $d=0.5$) difference between the two means. A two-tailed Type I error rate of 0.05 will be assumed.

In summary:

(1) For the power calculation, we focused on our primary hypothesis and outcome in Aim 1 to determine the sample size for our study ($n=162$); for the rest of other 4 Aims, we assessed the powers based on the sample size obtained in Aim 1. We showed that the proposed sample size will provide clinical meaningful effect size with enough statistical power for all the aims we planned to investigate;

(2) For model development and validation proposed in above aims, we will follow the general statistical model building strategy documented in detail in Harrell.¹¹³ Some major aspects we will consider are: (a) dealing with missing data by multiple imputing of missing predictor values to make good use of partial subject information, (b) allowing for nonlinear predictor effects using regression splines, (c) adjusting the variance-covariance matrix for multiple imputation, (d) graphically interpreting the model using partial effect plots and nomograms, (e) quantifying the clinical utility (discrimination ability) of the model, and (f) internally validating the calibration and discrimination of the model using the bootstrap to estimate the model's likely performance on a new observation of samples from the same sample stream.

6.3 Stratification factors and intervention allocation plan for randomized studies.

Randomization will be done using the minimization stratified randomization technique (QMinim). Minimization is designed to balance pre-identified stratifying covariates across treatment assignments more effectively than simple randomization.⁸⁷⁻⁸⁹ The covariates will be CG gender, CG age, and patient cancer type.

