If the patient and/or caregiver do NOT have email or internet access, informed consent will proceed via telephone with the patient and/or caregiver signing paper copies of the consent forms, previously provided by the medical staff. The patient and caregiver will mail the signed forms back to the researcher's office via a study-provided postage-paid envelope (also given at their health care provider visit) and will keep the unsigned copies. The enrollment procedure proceeds with contact information being completed via telephone.

Subjects' capacity to consent will be evaluated by the RA in conjunction with the clinical team. Participants must be cognitively intact, as evidenced by orientation to person, place, and time. They must be able to speak, read, and comprehend English.

All participants are volunteers and non-participation and withdrawal from the study are alternatives to study participation. Patients and caregivers will be told that they may withdraw from the study at any time. There are no risks to non-participation or withdrawal from the study. The RA will explain that participation or non-participation will have no effect on the care that the patient and caregiver will receive from the healthcare team.

For the extension period, caregivers will be offered an additional qualitative interview after completing the intervention. The consent form will give caregivers a choice to opt in and agree to be contacted for an interview. Caregivers randomized to the intervention will be selected for interviews using purposive sampling to select participants with a low score in at least one domain of the social determinants of health. Interviews will be done with 15 caregivers who opted in during the consent process. The interviews will take place after they have completed the intervention.

Once consent is obtained, baseline measures will be collected. All participants will be screened for health literacy using a 4-item Brief Health Literacy Screening Tool (BRIEF), a self-report tool that assesses comprehension to written and verbal health information as well as confidence in filling out medical forms. The research team will employ communication and teaching strategies from AHRQ's Health Literacy Universal Precautions Toolkit⁹⁴ for individuals identified as having limited health literacy.

Once baseline data have been obtained, the Project Director will randomly assign the CG to one of

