The Functional Assessment of Cancer Therapy - Lung (FACT-L, Version 4) is a 33-item questionnaire that measures self-reported HRQOL in patients with lung cancer over the last 7 days.^{104,105} Psychometric properties of the FACT-L were assessed by Cella et al.¹⁰⁴ in a sample of 116 patients with various types and stages of lung cancer. Internal consistency, construct validity, and sensitivity to change was established.

Interrupted Radiation Treatment Course, defined as the total number of missed treatment days due to patient or caregiver reasons, will be determined from the patient's radiation therapy treatment record. We will also record the duration (number of days) of each episode of absence from treatment.

Healthcare Utilization Outcomes

Healthcare utilization outcomes include unplanned hospital admission, unplanned emergency room visits, and unplanned IV fluid use for treatment of dehydration. We will evaluate the effects of the intervention, as compared to the control group, on these outcomes, as well as describe the costs associated with these outcomes. These outcomes will be measured at T2, T3, and T4.

Mediating Variable

Caregiver self-efficacy for caregiving will be measured with the Caregiver Inventory, a 21-item questionnaire that evaluates the domains of managing medical information, caring for the care recipient, caring for oneself, and managing difficult interactions and emotions.⁹⁹ This scale will be administered at all time points. Participants rate each item on a nine-point scale, ranging from *not at all confident* (1) to *totally confident* (9). Scores are summed, with higher scores indicating greater confidence. Psychometric properties of the Caregiver Inventory were initially reported on data from 133 family caregivers of terminally ill patients.⁹⁹ The Cronbach alpha was 0.91 and validity was supported through correlational analyses with other measures (Perceived Stress Scale and Caregiver Burden Inventory) as well as ratings by caregivers and social workers of caregiving tasks.⁹⁹

In addition, an investigator-constructed survey to measure self-efficacy for specific caregiving skills during radiation therapy will be used for descriptive purposes. Caregivers will rate their confidence in performing specific skills on a 10-point scale.

Covariates

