Patient illness factors – stage of cancer, time since diagnosis, treatment type (chemoradiotherapy vs. radiotherapy alone), HPV status (in HNC and anal cancer), use of palliative care, and patient performance status – will be recorded on the enrollment form. Updates for use of palliative care and patient performance status will be noted at T2, T3, and T4. Care demands, defined as hours/week spent caregiving, will be assessed at all time points. Demographic characteristics of both the patient and caregiver will be collected at baseline (T1). Use of mental health interventions (support group participation, social work and/or psychologist Involvement) will be assessed at all time points.

Three additional measures of social determinants of health are health insurance, social support, and financial toxicity. Health insurance will be assessed at baseline for patients and caregivers. Patient health insurance status will be obtained in the medical record, and caregiver insurance status will be obtained through self-report. Financial toxicity will be assessed with the Comprehensive Score for Financial Toxicity measure (COST), a patient-reported outcome measure that includes an 11-item scale and a single summary item of financial hardship. All items are rated on a 5-point Likert scale and lower scores indicate greater financial toxicity. The COST measure has been found to be reliable and valid in assessing caregiver financial toxicity. The 19-item Medical Outcomes Study (MOS) Social Support Survey will be used to measure perceived social support. The survey provides an overall support index score, as well as domain scores for emotional/informational, tangible, positive interaction, and affectionate support. Higher scores indicate greater support. The Ohio Opportunity Index (OOI), which measures health and well-being based on home address,

will be used to describe neighborhood characteristics for caregivers.

Other variables

Intervention dose, defined as the number of intervention sessions the caregiver receives, will be recorded at the completion of the intervention.

Other variables associated with cost analysis

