During the extension period, qualitative interviews will be conducted either in-person, by phone, or using UH Zoom based on caregiver preference. The interviewer will follow the interview guide, adding prompts and follow-up questions as appropriate. Interviews will last approximately 30 to 45 minutes. Interviews will be recorded and the data file will be uploaded to UH Box for storage.

Table 4. Study Measures

VARIABLE	INSTRUMENTS	TIME			
		T1	T2	T3	T4
CG Outcomes					
CG Anxiety	Patient Reported Outcomes Measurement Information System (PROMIS) ⁹⁵ Anxiety Short Form 7a	X	X	X	X
CG Depression	PROMIS ⁹⁵ Depression Short Form 8b	X	X	X	X
CG HRQOL	PROMIS ⁹⁵ Global Health Scale v.1.0/1.1	X	X	X	X
CG Fatigue	PROMIS ⁹⁵ Fatigue Short Form 7a	X	X	X	X
Patient Outcomes					
HRQOL	FACT-C, v. 4, ⁹⁶ FACT-E, v. 4, ⁹⁷ FACT-H&N, v. 4, ⁹⁸ and FACT-L, v. 4 ^{104, 105}	X	X	X	X
Interrupted radiation treatment course (total number of missed days from treatments)	Radiation Therapy PT treatment record		X		
Healthcare Utilization Outcomes					
Unplanned hospital admission	Hospital record		X	X	X
Unplanned emergency room visits	Hospital record		X	X	X
Unplanned intravenous fluid use	Hospital record (number of liter bags used)		X	X	X
Cognitive Mediator					
CG self-efficacy for caregiving	CG Inventory ⁹⁹	X	X	X	X
	Investigator-constructed self-efficacy scale for managing side effects & specific skills	X	X	X	X
Potential Moderators (Covariates)					
Patient Illness Factors (Stage; time since diagnosis; treatment type, e.g., concurrent chemotherapy; HPV status in HNC and anal cancer)	PT medical record	X			
Use of palliative care services	PT medical record	X	X	X	X
PT Performance Status	ECOG Performance Status ^{100,101} (patient)	X	X	X	X
Care Demands (hours/week spent caregiving)	Interview questions (CG)	X	X	X	X
Demographic characteristics (race, marital status, employment status, health insurance, socioeconomic status)	Interview questions (CG and PT)	X			
Use of mental health interventions (support group participation, social work and/or psychologist involvement)	Interview questions (CG and PT)	X	X	X	X
Financial toxicity	COST-FACIT (version 2)		X		X
Social support	MOS		X		

Note. PT = Patient; CG = Caregiver; ECOG = Eastern Cooperative Oncology Group; ADLs = Activities of daily living. CG age, CG gender, and PT cancer type will be used in the minimization stratified randomization technique. Number/types of care demands will be collected as descriptive data.

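### The primary T4 anxiety model adjusts for the Table 4 covariates without fixing a time point, so it can condition on values measured after randomisation

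*Combined protocol and SAP*

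**What the plan says.** Section 6.0 states that "An intent-to-treat analysis is planned". Under Aim 1 it defines the primary analysis as a repeated-measures linear mixed model with a contrast on anxiety at T4, "using baseline anxiety as a covariate, also adjusting for covariates described in Table 4". Adjustment for characteristics that differ at baseline is a separate, secondary analysis. Nothing in Section 6.0 or elsewhere limits the Table 4 covariates to T1.

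Table 4 (Section 5.4) has a block headed "Potential Moderators (Covariates". As extracted, it contains:

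- **T1 only:** illness factors (stage, time since diagnosis, treatment type, HPV status) and demographics, including insurance.
- **T1 to T4:** palliative care use, performance status, care demands, use of mental health interventions.
- **No T1 mark:** COST (T2 and T4) and MOS (T2).

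Section 5.2 also places COST and MOS under its Covariates heading: "Three additional measures of social determinants of health are health insurance, social support, and financial toxicity". For insurance it adds "Health insurance will be assessed at baseline for patients and caregivers"; it gives no time for the other two.

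Section 4.0 puts allocation after T1: "Once baseline data have been obtained, the Project Director will randomly assign the CG to one of" two groups. Every T2 or T4 value is therefore post-randomisation.

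**The concern.** An intent-to-treat contrast should estimate the total effect of assignment on T4 anxiety. Adjusting for something assignment has changed removes or distorts part of that effect, and the error can go in either direction.

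The protocol supplies a plausible route. In Table 3 (Section 5.3), the intervention sessions refer distressed caregivers to social work and identify sources of social support. Mental health service use and MOS measure closely related things.

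There is a second consequence. The amendment log dates the addition of COST and MOS to 4/5/22, and the Aim 4a text says that some social-determinant measures will exist only for the 96 extension participants. A model that requires these covariates could drop many randomised caregivers.

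Finally, leaving the time point open lets the covariate set be chosen after results are visible.

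**Working it through.** **1. Is the table reading safe?** The extraction agrees with the prose wherever it can be checked. Section 5.2 says of the utilisation outcomes "These outcomes will be measured at T2, T3, and T4", and those rows show T2 to T4. Care demands and mental health use are described as collected at every time point, and their rows show T1 to T4. The MOS mark falls in the same column as missed treatment days, which cannot be a T1 value. The columns should still be confirmed in the original.

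**2. The plan's own example of the mechanism (Aim 3, Power).** Total effect 0.40 SD, arm shift in self-efficacy 0.50 SD, correlation with anxiety 0.40:

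0.40 − 0.50 × 0.40 = 0.20 SD.

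This reproduces the stated figure. It is intended there, because mediation is the question, and self-efficacy is not in the covariate block. The same arithmetic applies to any shifted covariate in the primary model.

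**3. Illustration for a covariate collected throughout the trial.**

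From the documents: T1–T4 anxiety correlation 0.5 and 0.36 SD (Aim 1, Power); N = 214 (Section 3.0). The 0.36 is the plan's detectable difference, used here only as a convenient effect. (At 81 per arm I obtain (1.960 + 0.842) × 0.866 × √(2/81) = 0.381; that is a separate matter and nothing here depends on it.)

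Assumed: arm shift d, within-arm correlation ρ with T4 anxiety, and correlation c with T1 anxiety in the same direction as ρ.

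- Covariate slope: b = (ρ − 0.5c)/(1 − c²)
- Adjusted contrast: 0.36 ∓ d × b
- R² = (0.25 + ρ² − ρc)/(1 − c²)
- SE² = (1 − R²)(4/N)(1 + d²/[4(1 − c²)]); noncentral t, N − 4 df

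Worked case, d = ρ = 0.3 and c = 0: b = 0.3, R² = 0.34, SE = 0.112, contrast 0.36 ∓ 0.09.

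| d | ρ | c | Estimate (either sign) | Null rejection |
|---|---|---|---|---|
| 0 | any | any | 0.36 | 5% |
| 0.1 | 0.1 | 0 | 0.35 or 0.37 | 5.1% |
| 0.2 | 0.2 | 0 | 0.32 or 0.40 | 6.4% |
| 0.3 | 0.3 | 0 | 0.27 or 0.45 | 12.5% |
| 0.3 | 0.3 | 0.2 | 0.30 or 0.42 | 8.3% |
| 0.3 | 0.3 | 0.3 | 0.31 or 0.41 | 7.0% |

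Null means zero total effect. If the covariate itself causes anxiety, that requires an opposing direct effect; if the two only share unmeasured causes, it does not. A simulated repeated-measures fit over T2 to T4 (4,000 replicates, complete data, between-time correlations of 0.5 to 0.6 assumed) gave 0.274 or 0.449 and null rates of about 12% for the d = ρ = 0.3, c = 0 case.

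**4. Power without the covariate.** At N = 214 and 0.36 SD, the model with T1 anxiety alone has power 0.86. Adding an unshifted covariate with ρ = 0.3 gives 0.90, 0.88 or 0.87 for c = 0, 0.2 or 0.3.

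**5. COST and MOS under complete-case analysis.** Assume only extension participants have them: 96 × 0.88 ≈ 84. With ρ = 0.3, c = 0 and no shift, power is about 0.52, against 0.86 at N = 214 without them. At d = 0.3 the null rate for 84 is 7.9%.

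The count would be higher if parent-study caregivers followed after 4/5/22 also completed the surveys. Break-even, where residual variance over N is equal, is 214 × 0.66/0.75 ≈ 188 complete cases. That would need about 188 − 84 = 104 of the roughly 148 × 0.88 ≈ 130 analysed parent-study caregivers to have the measure.

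**The case against.** **COST and MOS may be drafting residue.** They were added in April 2022, Section 5.2 introduces them as social-determinant measures, and the covariate list in Section 1.2 omits them. The team may never have meant them for the primary model. This stands as a limit on confidence, but the operative sentence points to the table and the table now includes them.

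**Baseline values are the conventional reading for the rest.** Section 5.2 records palliative care use and performance status at enrolment and treats later values as updates. The Aim 4 text calls the primary model a basic ANCOVA, which ordinarily uses baseline covariates. For these two the point is mainly one of clarity. For mental health use it is weaker, since Aim 4 names use during treatment.

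**The arm difference may be small.** Section 5.63 has caregivers in either arm referred to social work above a depression threshold. This is fair, and it is why no size is claimed.

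**Missing predictors may be imputed.** Section 6.0 proposes multiple imputation of predictor values. If that were done for COST and MOS, neither the N = 214 nor the N = 84 figures would apply directly.

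Two stronger readings are tempting. A reader might apply the 12.5% null rate to COST and MOS; that figure assumes a covariate observed in all 214, which these cannot be. A reader might also infer that Aim 4a must be downgraded to description. Section 6.0 calls Aim 4 primarily exploratory, but gives Aim 4a its own power statement, and the wording of the primary model does not decide that question.

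**Conclusion.** The gap is real and lies in the primary analysis: the time point of the Table 4 covariates is not specified, and on a literal reading the model conditions on post-randomisation values. Confidence is high on the missing time point and moderate on whether COST and MOS would enter the model.

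A reader might conclude that the primary result will be biased. The documents do not support that. They give no expected arm difference in any of these covariates and no correlation with anxiety. Bias arises only if assignment shifts an adjusted covariate that is related to anxiety, and the smaller assumed shifts in the table do little harm. At the larger assumed values, the distortion is 0.05 to 0.09 SD on 0.36, with a null rate of 7.0% to 12.5%, for covariates collected throughout. For COST and MOS the more concrete risk is loss of sample, on the assumption of complete-case analysis. This should be fixed before unblinded analysis.

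**What to change.** In Section 6.0, Aim 1, replace the reference to Table 4 with a named list fixed before unblinded analysis: T1 anxiety; the minimisation factors (caregiver age, caregiver gender, patient cancer type); and any other listed covariate at its T1 value only. State that COST, MOS and all T2 to T4 covariate values stay out of the primary model. Confirm the COST and MOS columns in the original Table 4.

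In Aims 4 and 4a, COST, MOS and mental health use during treatment can still be analysed as planned. Add a sentence saying that they are measured after randomisation and cannot be read as baseline characteristics that identify who benefits.

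**Cost.** No new data. If an omitted later value of a covariate collected throughout is prognostic (ρ = 0.3) and unaffected by assignment, power falls from at most 0.90 to 0.86 in the modelled case. For COST and MOS under complete-case analysis, leaving them out raises power unless about 188 or more of the 214 have the measure (same assumed ρ, c = 0).

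### A secondary analysis of caregiver anxiety chooses its covariates by baseline significance tests; a fixed list that includes the minimisation factors would be better (minor; the primary analysis is not affected)

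*Combined protocol and SAP*

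**What the plan says.** Section 6.0, Aim 1, first defines the primary model. It is a linear mixed model for change in caregiver anxiety, "using baseline anxiety as a covariate, also adjusting for covariates described in Table 4", with the contrast at T4 (20 weeks after radiation) as the primary test.

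The same paragraph then adds a separate step. The arms are to be tested against each other on their characteristics at entry, and a further model, labelled secondary, is built from the results: "characteristics found to differ between groups at baseline will be adjusted for in the linear mixed model". It gives no list of characteristics and no threshold for a difference. It does not say whether the selected characteristics join the Table 4 covariates or replace them. The other caregiver outcomes are to be handled in a like manner, so the rule may extend to depression, HRQOL and fatigue.

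Allocation is by minimisation (sections 4.0 and 6.3). Among the potential moderators in Table 4 (section 5.4) are stage, time since diagnosis, treatment type, HPV status, performance status, care demands and several demographic variables. The minimisation factors appear only in the table's note: "CG age, CG gender, and PT cancer type will be used in the minimization stratified randomization technique".

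**The concern.** Allocation is random, so any baseline difference between arms arises by chance, and a test of it answers no open question. As a selection rule, the test looks only at imbalance. A strongly prognostic characteristic that happens to be balanced is left out, while an irrelevant one that happens to be unbalanced goes in.

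Three things follow:

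- The secondary model cannot be written down before the data are seen, so the second estimate placed beside the primary one depends on the data.
- The rule is nearly blind to the minimisation factors, because minimisation exists to balance them. These are the variables the design itself singles out as important.
- Precision that prespecified adjustment would bring is mostly given up in that analysis.

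What is at stake is the usefulness of a supporting analysis, not the primary test.

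**Working it through.** **Inputs from the documents (section 6.0, Aim 1 Power, unless noted).** 81 caregivers analysed per arm; two-sided 0.05; baseline-to-T4 correlation 0.50; detectable effect 0.36 SD adjusted and 0.41 SD unadjusted. Section 3.0 gives 214 for the final analysis after the extension, or 107 per arm if allocation is equal.

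**Assumptions, which the documents do not give.** Test threshold 0.05; 10 to 20 independent characteristics tested; one extra covariate, independent of baseline anxiety, correlated r = 0.2 to 0.3 with T4 anxiety.

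**1. The plan's own figure.** Detectable difference = (1.960 + 0.842) × SD × √(2/81).

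- Unadjusted (SD = 1): 0.440.
- Adjusted (SD = √(1 − 0.5²) = 0.866): 0.381.

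Power at 0.36 SD adjusted is Φ(0.36 / (0.866 × 0.1571) − 1.960) = 75.3%, so the stated 80% does not reproduce at 81 per arm. It does at 90 per arm (79.6%), that is, with all 180 randomised. This is a separate matter; here it only sets the starting value of 75.3%.

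**2. How often the rule selects something by chance.** P(at least one) = 1 − 0.95^k. For k = 10 this is 40%, with 0.5 selections expected. For k = 20 it is 64%, with 1.0 expected. Any given characteristic is selected about 5% of the time, however prognostic it is.

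**3. Test-then-adjust against prespecified adjustment, baseline anxiety always in the model.** With prespecified adjustment the residual variance is 0.75 − r².

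| r | Residual SD | Power at 0.36 SD, formula |
|---|---|---|
| 0 (baseline anxiety only) | 0.866 | 75.3% |
| 0.2 | 0.843 | 77.6% |
| 0.3 | 0.812 | 80.5% |

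Under the test rule, chance imbalance in the covariate stays in the estimate unless it passes ±1.96 standard errors. The share of the imbalance variance that stays is 0.95 − 2 × 1.96 × 0.0584 = 0.72. The variance ratio to prespecified adjustment is then about (0.75 − r² + 0.72 r²) / (0.75 − r²):

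- r = 0.2: 0.739 / 0.710 = 1.04.
- r = 0.3: 0.725 / 0.660 = 1.10.

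Simulation with the t test agrees. Test-then-adjust has about 75% power at both correlations, against about 76% (r = 0.2) and 79 to 80% (r = 0.3) with prespecified adjustment. The variance is about 3 to 11% larger. At 107 per arm the formula gives 86.0% with baseline anxiety only and 90.0% with the r = 0.3 covariate prespecified, so the gap is similar.

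**4. Selected characteristics added to a model that already holds the prognostic covariate (r = 0.3).** Simulated power falls from 79.5% to 79.0% with 10 non-prognostic characteristics tested, and from 79.4% to 77.9% with 20. Type I error stays near 0.05.

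**5. A balanced minimisation factor.** Take the idealised case of a perfectly balanced factor with r = 0.3. The rule never selected it. Leaving it out gave 76.0% power and type I error 0.037; adjusting for it gave 79.6% and 0.051. The omission makes the test conservative.

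**The case against.** The strongest reply is that the rule governs only a secondary analysis. The primary model is set out first, without reference to the tests, and already holds baseline anxiety and the Table 4 covariates, many of which are plausibly prognostic. On the natural reading, the selected characteristics are added to that model; the cost is then 0.5 to 1.5 points of power with no inflation of type I error. The larger gaps need covariates that predict anxiety beyond baseline anxiety and are not already in the model, and the documents give no such figures. All of this stands, and it limits the point to a minor one.

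A reader might infer a loss of about ten points: with an effect of 0.40 SD and a covariate correlated 0.5, test-then-adjust gives 73% against 83% with prespecified adjustment, and a variance about 22% larger. Those figures come from a model without baseline anxiety. The plan always includes baseline anxiety and assumes that same correlation for it: "Assuming a correlation of 0.50 between CG anxiety scores at baseline and T4". Most of that apparent loss is therefore the gain from a covariate the model already contains.

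A reader might also infer that the rule does nothing about imbalance or precision. In that same setting its power is 0.732 against 0.724 with no adjustment. It helps slightly, because it removes the largest imbalances, but it falls short of a fixed list.

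The reply does not remove two points. The secondary model still depends on test results that carry no information about prognosis. And adjustment for the minimisation factors is not clearly planned in either model, since Table 4 names them only in describing the randomisation.

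**Conclusion.** The point holds as a minor one. The plan states an inferior covariate-selection rule for a secondary analysis of caregiver anxiety, and possibly of the other caregiver outcomes. The rule selects chance differences, makes that model data-dependent and will rarely pick up caregiver gender, caregiver age or cancer type.

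Under the stated assumptions the cost is about 1 to 5 points of power against prespecified adjustment, or about 0.5 to 1.5 points if the selected characteristics only supplement a model that already holds the prognostic covariate. The 40 to 64% chance of at least one chance selection depends on the assumed 10 to 20 independent characteristics and 0.05 threshold.

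It would be wrong to conclude that the trial's main answer is at risk: the primary contrast does not use the rule, and none of the simulations showed type I error above about 0.05.

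**What to change.** In section 6.0, Aim 1:

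- Remove the two-sample baseline tests as a way of choosing covariates, and present baseline characteristics by arm descriptively.
- Define the secondary model before unblinding as baseline anxiety plus a fixed list of covariates measured at T1, including caregiver gender, caregiver age and patient cancer type. Where Table 4 shows repeated measurement (for example performance status or care demands), state that the T1 value is used.
- State that the same list applies to the other caregiver outcomes, with each outcome's own baseline value in place of baseline anxiety.

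The cost is a few degrees of freedom and a change of SAP wording. Data collection, sample size and the primary contrast stay as they are.
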